Study objectives	
Primary objectives: To predict the clinical prognosis according to the antiplatelet treatment regime (aspirin as first-line treatment or in combination with clopidogrel), develop an AI that will search for and retrieve similar cases to each patient, and assess benefits of the technology:
 
 1) To establish a stroke clinical-imaging library (big data) and develop Deep Learning-based AI that understands the relationship between anti-platelet agents and prognosis (progression or recurrence). AI will present the probability of stroke progression or recurrence following each treatment regime. AI will also help physicians make treatment decisions by searching for and retrieving existing cases with similar clinical conditions to the patients concerned. 2) To prove AI's merit in predicting prognosis by applying it to different patient groups. 
Secondary objective: To analyze practical results of antiplatelet agents: The aspirin alone group and the clopidogrel plus aspirin group will be compared against each other directly to help find the link between early progression and recurrence of stroke. Although this is a non-randomized trial, different statistical methodologies, including propensity score matching (PSM) should address confidence issues.

Study subjects	Acute ischemic stroke patients: Transient ischemic attack with confirmed acute ischemic stroke by brain imaging

Inclusion criteria	1) Male and/or female subjects who are aged 19 or over. 2) Patients with acute noncardiac stroke or transient ischemic attack within 72 hours of the onset (in the case of a transient ischemic attack, presence of ischemic/ischemic lesion on DWI or PWI). 3) Patients whose informed consent document within 72 hours of onset was signed and submitted. 4) Patients who were treated with aspirin alone or aspirin plus clopidogrel resinate following stroke.								

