Exclusion criteria	1) Patients who need anticoagulants for cardiac ischemic stroke or other reasons. 2) Patients who suffered severe stroke (National Institutes of Health Stroke Scale > 16). 3) Patients who received emergency remission therapies such as tPA and thrombolysis. 4) Patients with neurological deterioration prior to signing an informed written consent document. 5) Patients who have undergone patency procedures (surgery or stent insertion) in the cerebrovascular or carotid arteries following stroke or are expected to do so. 6) Patients who are scheduled to undergo major surgery. 7) Patients who developed stroke during procedure/surgery. 8) Patients with recent history (in the past three months) of cerebral hemorrhage. 9) Patients with active internal bleeding. 10) Patients with severe anemia (Hb <10 g / dL) or bleeding tendency (platelet <100,000 / uL or PT-INR > 1.7). 11) When a patient's life expectancy is less than 6 months due to other systemic disease.								
Number of target study subjects	
  
 	Aspirin alone group	Aspirin + Clopidogrel resinate group	Total No. of target subjects	
   
 No. of subjects	1,000	1,000	2,000	
  
		Aspirin alone group	Aspirin + Clopidogrel resinate group	Total No. of target subjects	No. of subjects	1,000	1,000	2,000
	Aspirin alone group	Aspirin + Clopidogrel resinate group	Total No. of target subjects						
No. of subjects	1,000	1,000	2,000						
Study duration	1) Study duration: Approximately 36 months from IRB approval (subject to change depending on subject enrollment speed) 2) Study duration for each subject: 90 days (\pm 15 days)								
Study drug and dose	
  
 Study drug	Route of administration/dose	
   
 Aspirin (monotherapy or concomitant therapy)	75~100mg once per day, initial loading dose of 300~500mg/d is allowed	
  
	Study drug	Route of administration/dose	Aspirin (monotherapy or concomitant therapy)	75~100mg once per day, initial loading dose of 300~500mg/d is allowed				
Study drug	Route of administration/dose								
Aspirin (monotherapy or concomitant therapy)	75~100mg once per day, initial loading dose of 300~500mg/d is allowed								

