Endpoints	
Primary study endpoints
 
AI will learn and predict the occurrence of the following outcome variables (up to 3 months after stroke onset) according to the antiplatelet regimen (aspirin alone, or aspirin plus clopidogrel). An independent investigator, without knowledge of individual patient treatment regimens, will evaluate the same outcome variables separately and compare the results with those predicted by the AI:
 
 1) Neurological deterioration 2) New ischemic stroke 3) Symptomatic hemorrhagic transformation of an ischemic stroke 4) Symptomatic intracranial hemorrhage 5) Myocardial infarction 6) Coronary revascularization without myocardial infarction 7) Major hemorrhage other than intracranial hemorrhage (life threatening or non-life-threatening) 8) Minor hemorrhage other than intracranial hemorrhage 9) Ischemic vascular death 10) Hemorrhagic vascular death 11) Other serious adverse events 
Secondary study endpoints
 
A direct comparison between the aspirin alone group and the aspirin and clopidogrel combination therapy group for the incidence of 11 outcome variables evaluated by an independent investigator at the primary endpoints will be conducted.

Statistical Methodology	
General principle
 
All the enrolled study subjects whose results are confirmed will be subject to analysis, and they will be selected and classified according to the study methodologies and objectives prior to analysis. During the study period, data will be regularly checked and managed so that the number of datasets and their levels will be maintained appropriately.
 
Analyses of endpoints
 
Analysis of primary endpoints
 
 1) The stroke clinical and imaging library (big data), that includes all the

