	
clinical/imaging information related to clinical prognoses, will be established, and based on a deep learning algorithm, AI that has learned the relationship between antiplatelet agents and the following prognostic information will be developed.
 
 2) A probability of prognosis according to each treatment option prior to using antiplatelet agents will be offered. This information will help physicians select an antiplatelet agent by searching for and retrieving similar cases that match each patient. 3) The stroke clinic and imaging library (big data) regarding the effect of antiplatelet agents that are being prescribed mainly to stroke patients in the clinical setting and the prognostic information of the patients concerned will be constructed. The relationship and prognostic features of antiplatelet agents in preventing early progression and recurrence of stroke will be extracted and analyzed from the “Big Data.” 4) The development of AI using deep learning techniques will provide the basis for analysis of internal and external variables of stroke. This technique will change the model composition in line with the features and numbers extracted from the data. The depth and structure of the model will segment and materialize the characteristics of the target subjects and will be accompanied by the optimal design and verification processes of the model to simultaneously consider clinical/image information. 5) The research analysis using the trained AI that will be developed will need to have its results clearly verified as to their quality/accuracy. The delivered outcome will be used directly or indirectly by physicians, but the performance and reliability of the results that will be generated are of significant importance. Therefore, the AI will learn and have its performance assessed based on the data that will continue to accumulate throughout this study. However, because of the features of deep learning technology, training and verification, using the same data may cause major issues such as overfitting. Therefore, a new dataset will be created to evaluate the performance of the AI. 
Analysis of secondary endpoints
 
 1) The propensity score matching (PSM) technique will be used to select either the aspirin monotherapy, or the clopidogrel resinate and aspirin combination therapy group which have matched important clinical/imaging parameters that affect the prognosis of stroke.

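### The AI's probability is offered for use before the first antiplatelet dose, but for patients treated before consent the cohort gives a risk of neurological deterioration conditional on none up to consent

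*Protocol*

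**What the plan says.** Synopsis, Statistical Methodology, Analysis of primary endpoints, item 2 promises: "A probability of prognosis according to each treatment option prior to using antiplatelet agents will be offered". It then gives the purpose: "This information will help physicians select an antiplatelet agent by searching for and retrieving similar cases that match each patient". Item 5 adds that "a new dataset will be created to evaluate the performance of the AI".

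Four other statements fix which patients and which events the AI can learn from:

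- Inclusion criterion 3 limits the time of consent: "Patients whose informed consent document within 72 hours of onset was signed and submitted".
- Inclusion criterion 4 sets the treatment condition: "Patients who were treated with aspirin alone or aspirin plus clopidogrel resinate following stroke".
- Exclusion criterion 4: "Patients with neurological deterioration prior to signing an informed written consent document".
- The Endpoints section of the synopsis describes the AI's task: "AI will learn and predict the occurrence of the following outcome variables (up to 3 months after stroke onset) according to the antiplatelet regimen". Neurological deterioration is the first of the eleven outcomes.

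No criterion puts consent before the first dose, and the Study description leaves the choice of drug to the attending physician in routine care. The endpoint text gives the end of the outcome window but no starting point.

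**The concern.** The probability is meant for the moment before any antiplatelet agent is given. The cohort is formed at consent, which may come later. A patient who starts a regimen, deteriorates and has not yet consented is excluded. A patient who starts the same regimen and stays stable until consent is included. For patients treated before consent, the data therefore describe those who have already passed through part of the early risk period.

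Early progression is the subject of the study. A physician using the output before the first dose could be shown too low a risk of the outcome that matters most at that time. Validation may not reveal this, because a test set drawn under the same criteria carries the same condition.

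**Working it through.** **No figure to reproduce.** The document gives no risk of deterioration, no timing of events and no interval from first dose to consent. The direction comes from the eligibility text. Every number below is an assumption or follows from one.

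**Formula.** Let r be the risk of deterioration counted from first dose, s the share of patients treated before consent, and q the share of their deteriorations that fall between first dose and consent. Those events remove the patient from numerator and denominator alike:

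cohort risk = r(1 − sq) / (1 − srq)

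**Assumed r = 8%:**

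| s | q = 10% | q = 25% | q = 50% |
|---|---|---|---|
| 100% | 7.3% | 6.1% | 4.2% |
| 50% | 7.6% | 7.1% | 6.1% |
| 25% | 7.8% | 7.5% | 7.1% |

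Example for s = 100%, q = 25%: 0.08 × 0.75 / (1 − 0.08 × 0.25) = 0.060 / 0.980 = 6.1%. If s = 0 or q = 0, the cohort risk equals r and there is no effect.

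**Range.** For r from 4% to 12% over the same s and q, cohort risk divided by true risk runs from 0.51 (r = 4%, s = 100%, q = 50%: 0.50 / 0.98) to 0.98 (r = 12%, s = 25%, q = 10%: 0.975 / 0.997).

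**What validation would show.** With s = 100% and r = 8%, a test set under the same criteria gives observed/predicted = 1.00. Patients assessed before the first dose would give 8 / 7.26 = 1.10, 8 / 6.12 = 1.31 or 8 / 4.17 = 1.92 for the three values of q.

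**Regimen comparison.** Assume s = 100% and true risks of 10% and 7% in the two groups, a risk ratio of 0.70.

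- q = 30% in both: 0.070 / 0.970 = 7.22% and 0.049 / 0.979 = 5.01%, ratio 0.69.
- q = 50% in the higher-risk group and 30% in the other: 5.26% and 5.01%, ratio 0.95.
- q = 30% in the higher-risk group and 50% in the other: 7.22% and 3.63%, ratio 0.50.

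The ratio barely moves if early loss is equal and moves a good deal if it is not.

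**Can a delayed-entry analysis recover the early risk?** This was simulated with 2,000 cohorts of 1,000 patients, an 8% risk, exponential event times with mean 2 days among those with an event, and entry independent of risk. Consent was uniform over 0 to 3 days after first dose, with 10% of patients consenting at first dose. The naive estimate averaged 4.7% (SD 0.7 points) and the delayed-entry estimate 8.0% (SD 1.4).

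This is a near-maximal case. The 72 hours run from onset, so a 3-day delay needs a first dose at onset. The share of events before consent is 0.9 × [1 − (1 − e^(−1.5)) / 1.5] = 0.9 × 0.482, about 43%.

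If consent is instead uniform over 1 to 3 days, so that nobody consents in the first day, delayed entry gives only 5.0%. That matches the exact risk given no event by day 1: 0.08e^(−0.5) / [1 − 0.08(1 − e^(−0.5))] = 5.01%.

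**The case against.** The strongest reply is that the effect may not exist. Inclusion criterion 4 can be read as naming the eligible regimens without fixing any order of dose and consent. A reader might infer that every patient enters already treated and that the AI's probability must be too low. The text does not support that: patients who consent before or at the first dose are unaffected, and their number is not given. This part stands, so the claim is that the probability could be too low.

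A reader might also extend the point to all eleven outcomes. Exclusion criterion 4 names only neurological deterioration, and the point is kept to that outcome.

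A third reply is that choosing an agent depends on the contrast between regimens, which survives if early loss is equal. That also stands. A reader might infer a biased comparison, but the document shows no difference in pre-consent loss by regimen.

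On validation, primary objective 2 speaks of applying the AI to other patient groups, and the Study description of independent test data. Neither says which eligibility criteria those data follow, so one can say neither that the test set hides the problem nor that it would reveal it.

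Finally, delayed-entry methods and rules for later changes of regimen can be left to a statistical analysis plan, which is not shown. That is fair for the methods. The mismatch itself lies between two statements in the protocol. An analysis plan cannot bring back excluded patients, nor recover risk from before the earliest consent.

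**Conclusion.** The point holds in a limited form. Followed as written, the protocol can deliver a different quantity from the one it promises. For patients treated before consent, it gives a risk of neurological deterioration conditional on being free of it at consent, not a risk before the first dose. Where some patients are treated and some deteriorate before consent, a probability used before the first dose could be too low for this outcome.

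The size is unknown and may be nil. Over the assumed ranges the cohort shows 0.51 to 0.98 of the true risk, and the low end needs every patient treated before consent and half of the events in that interval. Because the claim concerns the study's central subject and is cheap to limit, it should be corrected. Nothing here argues against exclusion criterion 4 itself.

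**What to change.** 1. **Analysis of primary endpoints, item 2.** State that the probability and the regimen comparison apply to patients free of neurological deterioration at consent. Add that use before the first dose is supported only if shown in patients who consented before or at first dose, or by a delayed-entry analysis from first dose.
2. **Primary study endpoints.** State that outcomes count from time zero, the later of consent and first dose, to 3 months after onset. Use the regimen in force at time zero as the group and as the AI's input. Time zero should not be consent for everyone: a patient untreated at consent would then be grouped by a regimen chosen later, possibly because of a deterioration in between. Report events between consent and first dose separately, without assigning them to a regimen.
3. **Data.** Record date and time of first dose, consent and deterioration, if the case report form (not shown) does not already do so.
4. **Screening log.** Count exclusions under criterion 4, by regimen, as far as the IRB allows.

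Exclusion criterion 4 stays. Sensitivity analyses for later changes of regimen can go in the statistical analysis plan.

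The cost is a narrower claim for the AI, a few sentences of text, up to three date-and-time fields and a short log. If delayed entry is used, precision falls (SD about 1.4 against 0.7 points in the simulation), entry must be assumed independent of risk, and risk before the earliest consent stays out of reach.

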	
Clopidogrel resinate (Concomitant therapy)
 
75mg once per day, initial loading dose of 300mg/d is allowed

Study description	
This is a pragmatic, multi-center, non-interventional, non-randomized prospective observational study.
 
■ Study procedures
 
This is a prospective study of patients with acute stroke or transient ischemic attack within 72 hours of symptom onset. It is to mainly observe the patients' prognosis following the prescription of clopidogrel resinate and aspirin, collect relevant data and create big data for stroke. Based on this data, an AI, using various advanced statistical methodologies and deep learning techniques will be developed, and offer information regarding stroke prognosis by extracting markers that are characteristic of the relationship between stroke and the study drug.
 
These analyses and results will include information on which drug regimen will better prevent the progression or recurrence of stroke by considering individual patient conditions. This is a pragmatic trial based on the prescription and treatment processes of routine clinical practice. Thus, there is no major restriction and with only the minimum exclusion criteria in place, it does not hinder usual clinical practices. Therefore, selecting and changing a patient's antiplatelet agents should be a rational medical judgment made by the patient's attending physician. The study will proceed without any major change in the sequence of routine clinical examinations, prescriptions, treatments, observations, etc. Provided, the process of storing and analyzing relevant information will be added to each study procedure in accordance with study methodologies and conditions no other special efforts or limitations will be required.
 
The data will be collected prospectively, and the AI will generate brain imaging data and prognostic indicators for 3-months after stroke has occurred. The performance of the AI will be verified with independent test sets.

Dropout criteria	
Because the subjects will receive usual stroke care practice, there will be no subject withdrawal or dropout due to issues related to the study description and design.
 
However, if a research subject withdraws his/her consent to participate in the study (informed consent to have his/her personal information utilized), participation of the research subject will be suspended, and the data concerned

	will not be used in the study.

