--	---

	2) Compare the prognosis of each treatment group to determine which prescription method is superior.
--	--

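### The protocol's secondary analysis commits to naming a superior regimen, which a matched comparison of physician-chosen treatments cannot support; it should report an adjusted association

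*Protocol*

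**What the plan says.** All references are to the Protocol Synopsis.

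- **Study description.** The design is stated plainly: "This is a pragmatic, multi-center, non-interventional, non-randomized prospective observational study". On treatment allocation, "selecting and changing a patient's antiplatelet agents should be a rational medical judgment made by the patient's attending physician".
- **Study objectives, secondary objective.** The two regimens are to be compared directly. On the lack of randomization it says: "Although this is a non-randomized trial, different statistical methodologies, including propensity score matching (PSM) should address confidence issues".
- **Endpoints, secondary.** A direct comparison of the two groups "for the incidence of 11 outcome variables evaluated by an independent investigator at the primary endpoints will be conducted".
- **Statistical Methodology, Analysis of secondary endpoints, item 1.** Propensity score matching is used to select groups "which have matched important clinical/imaging parameters that affect the prognosis of stroke". No other adjustment method is named.
- **Same section, item 2.** "Compare the prognosis of each treatment group to determine which prescription method is superior". No qualification is attached.

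**The concern.** When the physician chooses the drug, the choice can depend on how the physician judges the patient's risk of progression, recurrence or bleeding. Those judgments can also be related to outcome, which is confounding by indication. Matching on a propensity score balances the variables in the score. It leaves unbalanced any reason for prescribing that is neither in the score nor closely tied to something in it.

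Item 2 nevertheless sets the product of the matched comparison as a determination of which regimen is superior. An analyst who follows the text would turn a matched difference into a verdict about the drugs, although part or all of that difference could reflect who was prescribed what. This is the only direct comparison of the regimens in the protocol, so its wording decides what the study will be read as having shown about treatment.

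**Working it through.** **1. Figures in the plan.** The only relevant figure is the target of 1,000 per group (Number of target study subjects). The protocol gives no significance level, event rate or effect size, so there is no stated calculation to reproduce. Everything below except the 1,000 is an assumption, and using 1,000 as the matched number supposes that matching discards nobody.

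**2. Bias from one unmatched factor.** Let the true risk ratio (combination vs aspirin) be 1. Let a binary factor outside the score multiply risk by R, with prevalence c in the combination group and a in the aspirin group. The apparent risk ratio is

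[1 + (R − 1)c] / [1 + (R − 1)a].

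With R = 2 and c = 20%:

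- a = 30%: 1.2/1.3 = 0.92
- a = 40%: 1.2/1.4 = 0.86
- a = 50%: 1.2/1.5 = 0.80

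**3. Chance of p<0.05.** Take n per group, aspirin risk p₁ and apparent combination risk p₂ = p₁ × apparent RR. A pooled two-sided two-proportion test at an assumed 5% level rejects when the observed difference exceeds 1.96·√[2p̄(1 − p̄)/n], where p̄ is the mean of p₁ and p₂.

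Worked case: n = 1,000, p₁ = 0.10, a = 50%.

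- p₂ = 0.08 and p̄ = 0.09.
- Threshold = 1.96·√(2 × 0.09 × 0.91/1,000) = 1.96 × 0.0128 = 0.0251.
- Standard error of the difference = √[(0.10 × 0.90 + 0.08 × 0.92)/1,000] = 0.0128.
- Φ[(0.020 − 0.0251)/0.0128] ≈ 0.35. The opposite tail is negligible here.

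The same formula, with both tails, gives:

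| Aspirin-group risk | Matched per group | a = 30% | a = 40% | a = 50% |
|---|---|---|---|---|
| 10% | 1,000 | 9% | 20% | 35% |
| 2% | 1,000 | 6% | 8% | 10% |
| 5% | 1,000 | 7% | 12% | 19% |
| 15% | 1,000 | 11% | 28% | 50% |
| 10% | 600 | 7% | 14% | 23% |

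With equal prevalence (a = c) the chance is 5% throughout.

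**4. Direction and sample size.** The direction of bias cannot be known in advance. If the factor is instead in 40% of the combination group and 20% of the aspirin group, at 10% aspirin risk, the apparent RR is 1.4/1.2 = 1.17 and the chance of p<0.05 is 22% at 1,000 per group. It rises to 40% at 2,000 and 77% at 5,000. Larger numbers sharpen the estimate around the biased value.

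**5. Check that balancing measured variables does not cure this.** In a simulation of 200,000 patients with no treatment effect, one measured covariate and one unrecorded factor that doubled risk both influenced prescribing. The crude RR was 1.35. After balancing the measured covariate within 200 fine strata the RR was 1.16, because the unrecorded factor was still present in 41% of one group and 20% of the other.

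**The case against.** The strongest reply has five parts.

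- **The protocol does not claim that matching cures non-randomization.** The secondary objective opens by conceding the design and refers to "different statistical methodologies, including propensity score matching (PSM) should address confidence issues", with matching as one example. This stands as a reading of that sentence. It does not soften item 2, which draws its conclusion from the only method the protocol names.
- **No unrecorded prescribing reason is shown.** This stands. No covariate list is visible, and the library is described as holding all clinical and imaging information related to prognosis. A reader might infer that specific reasons for drug choice go uncollected, but the document does not support that. The point is narrower: matching offers no protection against a reason outside the score, and an unqualified verdict presumes there is none.
- **Sensitivity analyses belong in the SAP.** This stands. A reader might infer that the plan has no check for residual confounding, but the SAP is not shown and such a check may be in it. Adding one there would still leave the protocol's stated conclusion in place.
- **The illustration is favourable to the concern.** In part. Matching may discard patients, and some of the 11 outcomes are likely to be rarer than 10%. At 2% risk the chances are only slightly above 5%.
- **The outcome evaluator does not know the regimen.** True, and useful against assessment bias. It does nothing about differences between the patients who received each regimen.

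**Conclusion.** The point holds as one about the stated conclusion. Physician-chosen treatment, matching on selected clinical and imaging parameters, and an unqualified determination of superiority do not fit together. The design supports an adjusted association.

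The size is illustrative. With no true effect, a doubling of risk, and a 10 to 30 percentage-point imbalance in an unmatched factor, the apparent RR is 0.92 to 0.80. The chance of p<0.05 is 9% to 35% at 10% aspirin risk with 1,000 matched per group, and about 6% to 10% at 2% risk. The factor's existence, its strength, the event rates, the matched number and the test level are all assumed.

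Two stronger readings should be resisted. A reader might infer that a declared 5% error rate is breached, but the protocol declares no level. A reader might also infer that the eventual result will be wrong, but the document shows only that the design cannot exclude this explanation. The comparison is a secondary objective, and the planned evaluation of the AI on separate data is not directly affected.

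**What to change.** Reword item 2 of Analysis of secondary endpoints along these lines: *estimate the adjusted difference in incidence of each outcome between the matched groups, with 95% CI, as an association subject to residual confounding by indication*. Remove the clause that makes superiority the object of the comparison.

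Beside each estimate, report an E-value for the point estimate and for the confidence limit nearer to no effect. For RR ≥ 1 the E-value is RR + √[RR(RR − 1)]; for RR < 1, use 1/RR. For example, RR 1.35 gives 1.35 + √(1.35 × 0.35) = 2.04. This tells the reader how strong an unmatched factor would have to be to explain the estimate away.

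A negative-control outcome taken from outcome 11 (other serious adverse events) should not decide whether the comparison is labelled confounded. Nothing shows that these events are coded finely enough to isolate those unaffected by antiplatelets. At an assumed 2% rate, even the RR 0.80 bias would be detected only about 10% of the time, so a null result would reassure falsely. At a 5% level the rule would also misfire about 5% of the time by chance.

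The cost is a change of wording and a simple calculation, with no new data. The downside is a weaker headline claim for a secondary objective.
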